9.3.5.3 Objective Response Rate (ORR)

Objective response is defined as achieving a best overall response of CR or PR as determined per RECIST 1.1. The objective response rate (ORR) or proportion of subjects with an objective response and the corresponding exact binomial 95% CI will be calculated.

9.3.5.4 Disease Control Rate (DCR)

Disease control is defined as a best response of CR, PR, non-CR/non-PD (for subjects who have only non-target lesions), or SD per RECIST 1.1. The proportion of subjects who achieve a disease control response and the corresponding exact binomial 95% CI will be calculated.

9.3.5.5 Duration of Response (DOR)

DOR is defined as the time from the first confirmed objective response (CR or PR) to documented PD per RECIST 1.1 or death within 30 days of last dose of study drug (ZW25,

palbociclib, and/or fulvestrant) from any cause. Only subjects who achieve a confirmed objective response will be included in the analysis. Details of the censoring scheme for this analysis will be described in the SAP.

Kaplan-Meier plots and estimates of the quartiles and their corresponding 95% CIs will be computed.

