4.4.1 Discontinuation of Study Treatment

If any component(s) of the combination therapy is discontinued due to toxicity deemed related to the component(s), subjects on either part of the study may continue to receive the other component(s) of the study regimen until disease progression or start of subsequent anticancer therapy (Note: trastuzumab, alternate CDK4/6 inhibitors, or any other treatment not part of the study regimen will be considered subsequent anticancer therapy. Palliative radiotherapy to a non-target bone lesion that is not progressing is allowed after the second cycle of treatment and must be administered after the initial response assessment obtained per protocol. This will not be considered subsequent anticancer therapy but must not interfere with the assessment of tumor target lesions. Treatment with palbociclib should be interrupted during palliative radiotherapy). Subjects who discontinue treatment with all 3 drugs for any reason (except death or withdrawal of consent) on either part of the study will have an end-of-treatment (EOT) visit within 14 days after the last dose of study drug (ZW25, palbociclib, and/or fulvestrant) and safety follow-up visit at approximately 30 days after the last dose of study drug.

Study treatment may be discontinued for any of the following reasons:

- Adverse event (AE)
- Death
- Lost to follow-up
- Withdrawal of consent
- Physician decision (non-AE, non-progressive disease)
- Pregnancy
- Progressive disease (either radiographic or clinical progression)
- Protocol violation
- Study termination by sponsor
- Other, non-AE

Also, if a subject has not taken ZW25 for more than 4 weeks, he/she will be withdrawn from study treatment unless approval is obtained from the medical monitor to continue on study treatment.

Also, if a subject starts subsequent non-study anticancer therapy, then study treatment will be discontinued before the start of the new therapy

At a minimum, all efforts should be made for subjects to complete the EOT visit ([Section 6.4](#)) and the safety follow-up visit ([Section 6.5](#)), and efficacy ([Section 6.6](#)) and survival follow-ups ([Section 6.7](#)).

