6.6 Efficacy Follow-up (Every 8 weeks)

Subjects who have discontinued all study treatment on either part of the study for reasons other than progression or start of subsequent anticancer therapy will continue in follow-up with disease assessments approximately every 8 weeks after the previous scan until disease progression or start of subsequent anticancer therapy. The efficacy follow-up will include the following assessments:

- Disease assessment per RECIST 1.1 (CT/MRI scans, and breast cancer serum tumor markers [if being monitored])
- Bone scan (scintigraphy): For subjects with new lesions identified by post-baseline bone scintigraphy, targeted assessment by X ray, CT scan with bone windows, or MRI will be performed to confirm findings.
- Brain scan (MRI): After screening, brain scans will be required per protocol only for subjects with findings on the screening brain scan; for subjects without findings on the screening brain scan, subsequent brain scans will be done per institutional standard of care.
- ADA sample (only if a subject had an ongoing anti-ZW25 ADA present at the safety follow-up visit): These will be discontinued after the resolution of ADA.

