9.3.1 General Considerations

The primary efficacy analyses will be conducted after all subjects in Part 2 have either reached a progression-free survival time of at least 6 months or are considered to have a progression-free survival event (disease progression per RECIST v1.1, clinical progression or death) prior to 6 months, or are permanently censored for progression-free survival prior to 6 months. The final efficacy analyses will be conducted after all subjects have completed their treatment and the follow-up period or following study termination by the sponsor

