9.3.5.1 Progression-free Survival (PFS)

Progression-free survival (PFS) time is defined as the time from first dose of ZW25, palbociclib, and/or fulvestrant to the date of first documented disease progression (per RECIST 1.1) or death from any cause, whichever occurs first. Subjects who are alive and have not progressed at the time of the analysis will be censored at the time of their last evaluable tumor assessment. Subjects who have received subsequent anticancer therapy excluding radiotherapy without a prior reported progression will be censored at the time of their last evaluable tumor assessment on or prior to the initiation of first subsequent anticancer therapy. Details of the censoring scheme for this analysis will be described in the SAP.

Kaplan-Meier plots and estimates of the quartiles and their corresponding 95% confidence intervals will be computed.

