9.3.5.2 Progression-Free Survival at 6 Months (PFS6)

Progression-free survival at 6 months (PFS6) is defined as having a progression-free survival time ³ 24 weeks at the time of analysis where PFS time is defined as the time from the first dose of ZW25, palbociclib, and/or fulvestrant to the date of documented disease progression (per RECIST 1.1) or death from any cause. The percentage of subjects achieving PFS6 and the corresponding exact binomial 95% confidence interval (CI) will be calculated.

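### DOR counts a death only within 30 days of the last dose, while PFS and PFS6 count every death, so a late death without progression ends PFS but not DOR

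*Combined protocol and SAP*

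**What the plan says.** Section 9.3.5.5 starts DOR at the first confirmed CR or PR and follows it "to documented PD per RECIST 1.1 or death within 30 days of last dose of study drug", whatever the cause of that death. It restricts the analysis to confirmed responders, asks for Kaplan-Meier quartiles with 95% CIs, and adds: "Details of the censoring scheme for this analysis will be described in the SAP".

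The related definitions carry no such limit:
- Section 9.3.5.1 ends PFS at first documented progression "or death from any cause, whichever occurs first". Subjects who start subsequent anticancer therapy other than radiotherapy without prior progression are "censored at the time of their last evaluable tumor assessment on or prior to the initiation of first subsequent anticancer therapy".
- Section 9.3.5.2 ends PFS time for PFS6 at the "date of documented disease progression (per RECIST 1.1) or death from any cause".
- Appendix D ends PFS at progression or death. Its DOR paragraph ends only at objectively documented recurrence or progression.

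Under Section 6.6, subjects who stop all study treatment for reasons other than progression or new therapy "will continue in follow-up with disease assessments approximately every 8 weeks after the previous scan until disease progression or start of subsequent anticancer therapy".

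**The concern.** Death without progression ends a response just as it ends progression-free survival. Under the current text the same death in the same subject is a failure in one analysis and not in the other, and the protocol gives no reason for the difference. Appendix D adds a second DOR end event, so the protocol holds two versions and neither matches PFS.

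What is at stake is the reported DOR curve and median. Kaplan-Meier censoring assumes that a censored subject would have gone on like those still at risk. That cannot be so for a subject who left the risk set by dying. The effect would usually be a DOR that looks longer than the responses were.

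**Working it through.** The plan gives no DOR figure to reproduce, so the check compares definitions and then adds an illustration on assumed data.

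**Step 1: can the case arise?** Section 4.4.1 allows treatment to stop for an adverse event or by physician decision. Section 6.6 then schedules scans about every 8 weeks, which is 8 × 7 = 56 days. A responder can thus be off all drugs, without progression and still under efficacy follow-up, well beyond 30 days.

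**Step 2: apply the definitions.** Take a confirmed responder who stops all three drugs without RECIST progression.

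| Course after last dose | PFS (9.3.5.1) | DOR (9.3.5.5) |
|---|---|---|
| Dies on day 20, no new therapy | Event | Event |
| Dies on day 60, no new therapy | Event | Not an event |
| Starts new anticancer therapy, then dies on day 60 | Censored before new therapy | Not an event |

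Only the second row shows the mismatch. For PFS6 a death of this kind matters only if it comes before 24 weeks.

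**Step 3: direction if the late death is censored at death.** Let n subjects be at risk just before the death. Counting the death multiplies the survival estimate by (n − 1)/n, and censoring it multiplies by 1. The later risk sets are the same either way. So for n > 1 the censored curve equals the counted curve times n/(n − 1) from that time on, and it is never lower. The median rises or stays where it was.

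**Step 4: hand example (assumed data).** Five responders: progression at 4, 8, 12 and 16 months, one late death at 6.
- Death counted: S(4) = 4/5 = 0.80; S(6) = 0.80 × 3/4 = 0.60; S(8) = 0.60 × 2/3 = 0.40. The median is 8 months.
- Death censored at 6: S(4) = 0.80; S(8) = 0.80 × 2/3 = 0.533; S(12) = 0.533 × 1/2 = 0.267. The median is 12 months.
- Censored instead at a last scan at 5.5 months, the risk sets at 8 and 12 are the same, and the median is again 12.

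S never equals exactly 0.5 here, so the result does not depend on how ties at the median are handled.

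**Step 5: range under a simple model (assumed).** Suppose constant hazards, a median of M months with all deaths counted, and a share s of DOR events that are late deaths without progression. Censoring them leaves the hazard (1 − s) × ln 2 / M, so the median becomes M/(1 − s). With M = 12:
- s = 5%: 12/0.95 = 12.6
- s = 10%: 12/0.90 = 13.3
- s = 20%: 12/0.80 = 15.0
- s = 30%: 12/0.70 = 17.1

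With s = 0 nothing changes. The documents give neither M nor s.

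**The case against.** The best defence is that the limit is deliberate and the SAP deals with the rest. Appendix H records that Amendment 4 changed the DOR definition to agree with the SAP. Section 9.3 lets the SAP describe departures from the protocol's methods. The document reviewed here does not include the SAP's DOR text, so how a late death is handled cannot be checked. This stands in part. It would be too strong to say that the SAP cannot repair the gap, and censoring is an inference. However, Section 9.3.5.5 defers only the censoring scheme, while the list of events is fixed there. Agreement with the SAP also does not explain why death is treated differently in DOR and PFS.

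A second defence is that late deaths are confounded by later treatment. The PFS rule already deals with that by censoring before new therapy, and the same rule can serve DOR.

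A third is that no passage requires DOR and PFS to share a death rule, and that the affected group is narrow. Both are true, and they are why the priority is low.

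**Conclusion.** The mismatch holds on the current text: a late death without progression or new therapy is a PFS event and not a DOR event. If it is censored and scans continue as Section 6.6 requires, Kaplan-Meier DOR would generally be overstated or unchanged. The size is unknown and may be zero, because the documents give no number of responders, of stops without progression or of late deaths. The 8-versus-12 example and the M/(1 − s) range show direction under assumed inputs and are not forecasts.

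Three stronger readings are not supported:
- A reader might infer that the efficacy conclusions are compromised. DOR is a secondary, descriptive endpoint, and PFS6, PFS and OS use their own definitions.
- A reader might infer that the median DOR could equally well fall, with censoring at a last scan long before death. That needs scan gaps longer than Section 6.6 schedules for these subjects, and in small samples the result can turn on a tie convention that the protocol does not state.
- A reader might fold in clinical progression, since Section 9.3.1 speaks of a "progression-free survival event (disease progression per RECIST v1.1, clinical progression or death) prior to 6 months" while 9.3.5.1 and 9.3.5.2 name only RECIST progression and death. That inconsistency, and any PFS rule for deaths after scans stop, touch the primary endpoint and should be raised separately.

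**What to change.** In Section 9.3.5.5, delete the words that confine death to the 30 days after the last dose, together with the bracketed drug list. DOR then ends at documented RECIST 1.1 progression "or death from any cause, whichever occurs first".

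Add the censoring rule of Section 9.3.5.1: a responder who starts subsequent anticancer therapy (excluding radiotherapy) without prior progression is "censored at the time of their last evaluable tumor assessment on or prior to the initiation of first subsequent anticancer therapy". Without that sentence, removing the limit would make deaths after new therapy count in DOR but not in PFS.

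Align the DOR end event in Appendix D and in the SAP. If the 30-day version is wanted, keep it only as a labelled sensitivity analysis.

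The cost is one deleted phrase, one added sentence and matching edits in Appendix D and the SAP. No new data are needed, since deaths are already collected for PFS and OS. The downside is that reported DOR may be slightly shorter.

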9.3.5.6 Overall Survival (OS)

OS is defined as time from first dose of ZW25, palbociclib, and/or fulvestrant until death from any cause. Subjects who did not achieve the event (death) at the time of the analysis or are lost to follow-up will be censored at the date they were last known to be alive (i.e., right censored). Imputation for partial or missing dates of death or last contact and details of the censoring scheme will be described in the SAP.

Kaplan-Meier plots and estimates of the quartiles and their corresponding 95% CIs will be computed.

9.3.6 Pharmacokinetic Analyses

PK analyses will be performed based on PK analysis set as defined in [Section 9.2](#).

PK concentrations and PK parameters will be summarized using descriptive statistics (i.e., n, arithmetic mean, geometric mean, median, standard deviation, range, coefficient of variance) by ZW25 dose and presented graphically as individual and mean plots.

The following PK parameters will be derived for single dose using extensive PK sampling data after dose 1:

- $C_{\max,1}$: maximum observed serum concentration
- $t_{\max,1}$: time to maximum observed serum concentration
- AUC_{0-t} : area under the serum concentration-time curve from zero to the last measurable concentration
- λ_z : terminal elimination rate constant
- $t_{1/2}$: apparent elimination half-life
- $AUC_{0-\infty}$: area under the serum concentration-time curve from zero to infinity
- CL: serum clearance
- V_d : volume of distribution in the terminal elimination phase

Elimination parameters will be calculated if data allow to meet standard PK acceptance criteria.

The following PK parameters will be derived for multiple dosing using PK sampling data after all doses for subjects in Part 1 and subjects with extensive PK sampling in Part 2 only:

- C_{ave} : average concentration over dosing interval

The following parameters will be derived and summarized for all subjects in all Parts using sparse sampling data:

- C_{\max} : maximum observed serum concentration

- C_{\min} : minimum observed serum concentration (trough)
- $R_{C_{\min}}$: accumulation index, calculated as C_{\min} (last dose)/ C_{\min} (first dose)
- $C_{\text{trough,ss}}$: trough concentration at steady state

The attainment of steady state will be determined by repeated measures analysis of variance (ANOVA) using aggregate assessment of trough concentrations.

Dose proportionality will be assessed by appropriate statistical methods based on amount of available data. Single dose PK parameters as well as multiple dose parameters will be used in these analyses.

Further details of PK analysis will be described in the SAP.

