In non-GLP pharmacokinetic (PK) and GLP TK studies, ZW25 serum exposure increased with dose (5 mg/kg through 150 mg/kg IV) in cynomolgus monkeys. ZW25 was mostly distributed to the serum compartment and was cleared slowly from the serum. Mean half-life of ZW25 after either a single dose or repeat doses ranged from 74.3 to 215 hours (2.73 to 8.95 days) and was similar to the reported half-life (3 to 14 days) of trastuzumab from repeat-dose studies in rhesus and cynomolgus monkeys (EMEA 2005). Cohorts from all dosing levels of the GLP toxicology study of ZW25 were screened for antidrug antibodies (ADA). Only 2 of the 292 samples tested were confirmed positive; however, the majority of ZW25-treated animals had serum concentrations that exceeded the specific drug tolerance level of the assay. Thus, ADA may be present but undetectable due to high drug concentrations.

The GLP toxicology study evaluated the toxicity and toxicokinetics (TK) of weekly ZW25 at doses of 5, 50, and 150 mg/kg for 8 and 13 weeks. ZW25 was well tolerated and no adverse effects were observed at weekly doses up to 150 mg/kg IV for up to 13 weeks.

The nonclinical program supported evaluation of ZW25 as an IV infusion in the clinic. Therefore, a first-in-human clinical study was initiated in September 2016. This ongoing, multi-part, Phase 1 study (ZWI-ZW25-101) is evaluating the safety, pharmacokinetics (PK), immunogenicity, and anti-tumor activity of ZW25 as a single agent and in combination with selected chemotherapy agents in subjects with locally advanced (unresectable) and/or metastatic HER2-expressing tumors.

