5.2.3 Dose Modifications of ZW25

An individual subject who experiences an event that meets the criteria for DLT (defined in [Section 3.1.2](#)) at any time on study treatment may continue at a step-down dose (or an intermediate dose level determined by the SMC) once the toxicity has returned to Grade 1 or baseline with approval of the medical monitor. If the subject then experiences another such event at the step-

down dose level, with approval from the medical monitor, the dose of ZW25 administered to that individual subject should be reduced again but should not go below 10 mg/kg Q2W.

For Part 2 of the study, dose modifications for ZW25-associated toxicity are presented in [Table 5](#) below. Dose decreases or delays for other reasons may be permitted with approval from the medical monitor. The reason for dose decrease or delay must be recorded, and the sponsor must be notified. Up to 2 dose reductions per subject will be allowed for Q2W dosing, but the reduced dose cannot be lower than 10 mg/kg Q2W.

There must be a minimum of 10 days (± 2 days) between doses. Day 15 doses not administered within 6 days after Day 15 must be skipped.

Note: Although only 1 step-down dose level (not lower than 15 mg/kg Q2W) of ZW25 is allowed in the study at a cohort level, individual subjects may have up to 2 dose reductions as long as the reduced dose is not lower than 10 mg/kg Q2W.

Table 5: Recommended Management and Potential Dose Modifications for ZW25-Associated Toxicity

Adverse Event Related to ZW25	Action for ZW25
Grade 1 or Grade 2 nausea and vomiting	
 • Suggest a 5-hydroxytryptamine (5-HT₃) receptor antagonist until resolution of symptoms, or a prochlorperazine. • No dose modification of ZW25 is required. • For breakthrough nausea or vomiting, consider olanzapine 5 or 10 mg daily for three days. For subjects already receiving olanzapine, prochlorperazine may be used.

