APPENDIX B: PHARMACOKINETIC EXTENSIVE SAMPLING TIMEPOINTS

Time	Cycle 1 (4 Weeks)							Cycle 2 (4 Weeks)		Every even-numbered cycle thereafter (4 Weeks)		EOT		
	D1				D2	D5	D15		D1 and D15		D1			
	Pre- dose ^a	End of ZW25 infusion	2 h post- dose ^b	4 h post- dose ^b	8 h post- dose ^b	24 h post- dose ^b	96 h post- dose ^b	Pre- dose ^a	End of ZW25 infusion	Pre- dose ^a	End of ZW25 infusion		Pre- dose ^a	End of ZW25 infusion
Allowed time window		+15 min	± 15 min	± 15 min	± 15 min	±4 h	± 4 h	- 4 h	+15 min	- 4 h	+15 min	- 4 h	+15 min	
PK serum sample	X	X	X	X	X	X	X	X	X	X	X	X	X	X ^c

D = day; EOT = End of Treatment; PK = pharmacokinetics

All subjects in Part 1 and at least 6 subjects in Part 2.

^a Relative to the start of ZW25 infusion

^b Relative to the end of ZW25 infusion

^c Only required if the subject has completed less than 6 months of treatment

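### Single-dose AUC0-t in Section 9.3.6 has no common end point: it follows the day of dose 2, which shifts it by about 4% to 17% within the visit window and by up to about 30% at the extremes of permitted timing

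*Combined protocol and SAP*

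**What the plan says.** Section 9.3.6 introduces the single-dose list with "The following PK parameters will be derived for single dose using extensive PK sampling data after dose 1". The list includes AUC0-t, defined as the "area under the serum concentration-time curve from zero to the last measurable concentration", and AUC0-∞. The parameters are summarised by ZW25 dose. On proportionality the section says "Dose proportionality will be assessed by appropriate statistical methods based on amount of available data", and it names the single-dose parameters among the inputs.

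After dose 1, Appendix B samples at the end of infusion and at 2, 4, 8, 24 and 96 h, then at Day 15 predose. Its footnote ties predose samples to the infusion: "Relative to the start of ZW25 infusion", with a window of 4 h before.

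Appendix A gives the Day 15 visit a window of 2 days either side. Section 5.2.3 also allows later dosing: "Day 15 doses not administered within 6 days after Day 15 must be skipped". After Day 15, the next scheduled PK sample for a subject who continues is Cycle 2 Day 1 predose.

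On AUC0-∞ and the other terminal-phase quantities, Section 9.3.6 adds a condition: "Elimination parameters will be calculated if data allow to meet standard PK acceptance criteria".

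**The concern.** An AUC that stops at the last measurable sample is comparable between subjects only if they all stop at about the same time, or if little area remains after the last sample. Neither is assured here. The plan itself expects a measurable trough after dose 1, because the accumulation index in Section 9.3.6 divides by the first-dose Cmin. The end of the interval is therefore set by when dose 2 is given.

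A predose sample before a late dose lies inside its PK window, so the review of sampling deviations in Section 7.3 would not flag it. Using actual times, as Section 7.3 requires, puts the sample at the right place on the time axis but does not give subjects a common end point.

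Single-dose PK parameters are secondary endpoints in both parts. If dose cohorts differ in their Day 15 timing, part of any difference in AUC0-t between doses, or part of its absence, would come from the calendar and not from exposure.

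**Working it through.** The plan states no figure for the spread of AUC0-t, so there is none to reproduce.

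**Inputs**
- End of the interval: 12 to 16 days after dose 1 (Day 15 ± 2 days, Appendix A); up to 20 days (dosing to Day 21, Section 5.2.3); about 28 days if the Day 15 dose is skipped and the next sample is Cycle 2 Day 1 predose.
- Half-life: the documents give only monkey data. Section 1.4 says "Mean half-life of ZW25 after either a single dose or repeat doses ranged from 74.3 to 215 hours (2.73 to 8.95 days". By arithmetic 215/24 = 8.96 days, which agrees with the text, but 74.3/24 = 3.10 days, not 2.73. I use 3.10 and 8.95 days as an assumed range.
- Dose contrast: 20/15 = 1.333, the largest that cohort-level dosing allows.

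**Model.** With mono-exponential decline, the share of AUC0-∞ captured by day t at half-life h is F(t) = 1 − exp(−ln 2 × t / h).

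| Half-life | F(4) | F(12) | F(14) | F(16) | F(20) | F(28) |
|---|---|---|---|---|---|---|
| 3.10 d | 0.591 | 0.932 | 0.956 | 0.972 | 0.989 | 0.998 |
| 8.95 d | 0.266 | 0.605 | 0.662 | 0.710 | 0.788 | 0.886 |

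For two subjects with the same dose and the same PK, the AUC0-t ratio is F(late)/F(early):

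| Comparison | 3.10 d | 8.95 d |
|---|---|---|
| 16 vs 12 days (visit window) | 1.04 | 1.17 |
| 20 vs 14 days (latest vs nominal) | 1.03 | 1.19 |
| 20 vs 12 days (extremes) | 1.06 | 1.30 |
| 28 vs 14 days (Day 15 skipped vs nominal) | 1.04 | 1.34 |

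**Against the dose contrast.** On the log scale, ln(1.301)/ln(1.333) = 0.92, so the extreme pair at 8.95 days covers 92% of the contrast; at 3.10 days it covers 21%. For the visit window the shares are 56% and 15%. At 8.95 days, 15 mg/kg sampled at 20 days gives 0.75 × 1.301 = 0.98 of the AUC0-t of 20 mg/kg sampled at 12 days.

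**Average spread.** If draws were spread evenly over 12 to 20 days (an assumption), the CV of AUC0-t from timing alone would be 1.7% at 3.10 days and 7.4% at 8.95 days.

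**Sensitivity**
- The 20-vs-12-day ratio reaches 1.333 at a half-life of about 10.2 days. At an assumed 14 days it is 1.40.
- The 16-vs-12-day ratio stays below 16/12 = 1.333 at any finite half-life.
- Section 9.3.6 names no trapezoidal rule. On the Appendix B times, with a 2 h infusion assumed, a linear rule gives 1.31 and 1.38 for 20 vs 12 days; a log-down rule gives 1.06 and 1.30.

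**AUC0-∞ as a fallback.** At 8.95 days the extrapolated share is 1 − 0.788 = 21% for a 20-day draw and 1 − 0.605 = 39% for a 12-day draw. At 3.10 days it is 1% to 7%.

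**The case against.** The strongest reply concerns size. A ratio near the dose contrast needs one subject at each end of permitted timing together with the longest cited half-life, or a linear trapezoid across the gap after 96 h. Within the visit window, at the short half-life, the effect is 4%. The human half-life is not in the documents. This stands, and the size has to be given as a range.

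The plan also has safeguards. AUC0-∞ has a common end point, Cave averages over the dosing interval for multiple doses, and the PK set in Section 9.2 requires sufficient samples and allows exclusions for deviations. These help only in part. AUC0-∞ is conditional on acceptance criteria, Cave is not a single-dose measure, and permitted late dosing is not a deviation.

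Section 9.3.6 leaves further detail to the SAP, whose text is not in the documents reviewed. A fixed-interval AUC may already be there, so it cannot be called absent from the whole plan. What can be said is that the protocol's stated rule does not provide one.

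The consequence is limited too. The dose contrast exists only if a step-down cohort opens, and it is smaller for a dose between 15 and 20 mg/kg. Under Section 3.1.2 the recommended dose rests on DLTs, overall safety and the SMC's recommendation, not on AUC. This stands and keeps the point a minor one.

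**Conclusion.** The mechanism holds: AUC0-t as defined runs over an interval set by the date of dose 2, and it enters by-dose summaries and dose proportionality. For identical exposure the difference is about 4% to 17% within the visit window and at most about 30% between 12-day and 20-day draws, against a conditional contrast of 33%. These figures rest on mono-exponential decline and monkey half-lives of 3.1 to 8.95 days; a longer human half-life would raise them.

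A reader might infer more than the documents support:
- **That timing routinely rivals the dose effect.** It does so only for an extreme pair; the average CV is about 2% to 7%.
- **That a skipped Day 15 dose cuts AUC0-t off at 96 h**, at 0.591/0.956 = 62% or 0.266/0.662 = 40% of the 14-day area. For a subject who continues, the Cycle 2 Day 1 predose sample still lies on the dose-1 curve, so the area grows instead. Truncation at 96 h needs there to be no later dose-1 sample at all.
- **That the early edge is below 12 days** because Section 5.2.3 says "There must be a minimum of 10 days (± 2 days) between doses". The Day 15 visit window in Appendix A is tighter.
- **That delays for toxicity bias the comparison.** This is plausible, but nothing in the documents shows it.

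This is a low-cost improvement, not a flaw that threatens the trial's conclusions.

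**What to change.** In Section 9.3.6 and the SAP:
1. Add AUC0-336h, the area over a fixed 14-day interval after dose 1. Obtain the value at 336 h by log-linear interpolation, or by short extrapolation, from the actual sample time.
2. Use AUC0-336h in place of AUC0-t for the by-dose summaries and for dose proportionality.
3. Set it to missing when no dose-1 sample exists beyond 96 h.
4. Keep AUC0-t as a reported or listed parameter.
5. State the trapezoidal rule.

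Subjects with identical PK then have a ratio of 1.00 by construction under the model, and the 20 vs 15 mg/kg contrast stays at 1.333.

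The cost is wording in the SAP and in protocol Section 9.3.6. No sample, visit or dosing rule changes. An early Day 15 draw needs up to 2 days of extrapolation: for a 12-day draw that is 1 − 0.9317/0.9563 = 2.6% of the 14-day area at 3.10 days and 1 − 0.6052/0.6618 = 8.6% at 8.95 days. After a skipped Day 15 dose the interpolation spans 96 h to about 28 days and leans harder on log-linear decline, so those values should be flagged. An occasional subject will have a missing value.
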